2.10.3 IMP Storage, Dispensing and Destruction

A shelf-life of minimum 6 months will be assigned to the trial packs (subject to MHRA approval). A 24 month ICH stability study will be run in parallel and a shelf-life extension program can be considered.

IMP packs will be stored in the storage room at ambulance stations as well as on vehicles as per normal practice.

The number of IMP packs “dispensed” on each vehicle may vary between ambulance services and within ambulance services and will be detailed in the trial operations manual.

Any syringes not used within the trial IMP pack will be destroyed as per local ambulance service operations and documented.

2.10.4 IMP Accountability and Monitoring

All uses of trial IMP packs will be documented on accountability logs. The trial will utilise the ambulance services systems for documenting receipt, dispensing, returns and destruction of IMP packs.

The attending clinician will be required to document on the patient record the IMP pack number how many syringes were used from the IMP pack.

Trial IMP will be reconciled where possible on station and also with the trial database which detail patients who have been enrolled and the trial IMP packs that were used.

2.10.5 Training

A programme of training will be provided to ambulance personnel and air ambulance staff (where relevant) participating in the trial. This will include the following:

- Trial background
- Randomisation procedures
- Basic GCP principles
- Inclusion and exclusion criteria
- Data collection and documentation
- Ethical issues and consent

In addition all training information and training materials will be made available via the trial website. Each Trust will record and maintain training logs and report a summary to the WCTU.

3. METHODS AND ASSESSMENTS

3.1 Schedule of delivery of intervention and data collection

Table 1

	Day 0 Cardiac Arrest	Hospital	Day 30	Week 6 Letter to Patient (if missed in hospital)	Month 3 (2-4) Follow up visit	Month 6 (5-10*) Postal	Month 12 (12)
Inclusion/ Exclusion Criteria	✓	x	x	x	x	x	x
Cardiac Arrest Data	✓	x	x	x	x	x	x
Patient Identifiers (if applicable)	✓	✓	x	x	x	x	x
Adverse Event Reporting	✓	✓	x	x	x	x	x
Survival Checks	✓	✓	x	✓	x	x	✓
Survival Status	✓	✓	✓	x	✓	✓	✓
Quality of CPR	✓	x	x	x	x	x	x
Hospital stay data (LoS)	x	✓	x	x	x	x	x
Neurological Outcome mRS	x	✓	x	x	✓	✓	x
Notification of enrolment and invitation to take part in the follow up	x	✓	x	✓	x	x	x
Informed Consent	x	✓	x	x	✓	x	x
Neurological outcomes: IQCODE and 2 simple questions	x	x	x	x	✓	✓	x
Health Economics Questionnaire	x	x	x	x	✓	✓	x
Quality of Life Questionnaires: SF-12 and EQ-5D	x	x	x	x	✓	✓	x
Functional outcomes: MMSE, HADS, PTSD	x	x	x	x	✓	x	x

*The 6 month data collection window can be longer in the early part of the trial but for patients enrolled in month 36, data will need to be retrieved at 6 months.

3.2 Data collection

3.2.1 Patient Enrolment

All cardiac arrests where a trial pack is opened will be reported to the WCTU promptly. Mechanisms for providing this information will be specific to each ambulance service.

3.2.2 Hospital

Patients may be taken to any hospital in the trial regions. Although hospital clinicians will not have a role in delivering the trial interventions, they will be informed about the trial and will be provided with information about the trial for any clinicians or patients that need it.

Hospitals will be contacted initially to ascertain survival of patients handed over from ambulance services to the ED. If the patient has survived, the research paramedics will liaise with the hospital clinicians to visit the patient and seek consent for continuation in the study (see Section 2.6.10).

For any patient taken to hospital we will seek data on survival, length of stay in hospital and on ICU, targeted temperature management, adrenaline use and mRS score at discharge as well as discharge address and GP details. As some patients are found in a public place without any identifiers or only part of their details are known to the ambulance service at the time of arrest, hospitals will also, where necessary, provide missing information such as name, address, date of birth.

3.2.3 Follow-up

Survivors willing to take part will be followed up approximately 3 months and 6 months after their cardiac arrest as per table 1. Wherever possible the 3 month assessment will be by home visit, but if the patient prefers postal questionnaires or to go through the questionnaires over the telephone this can be arranged although MMSE cannot be done over the phone. Data for the 6 month follow up will be issued from WCTU and returned by post.

Following the approach to the patient, in the unlikely event that we have not obtained a response from the patient after 1 month, we will approach the patient's GP or hospital or ambulance service for information on their mRS score as close to 3 and 6 month time points as possible.

Where we have not been able to collect data about the patient's stay in hospital such as length of stay on ICU, this will be collected from electronic data sets such as Intensive Care National Audit and Research Centre (ICNARC), National Institute for Cardiovascular Outcomes Research (NICOR) and or Hospital Episode Statistics (HES). These data sets will also be used for the health economic analysis.

3.2.4 Quality of CPR

Information on CPR quality is increasingly being collected by NHS Ambulance Services.

Trial sites that collect these data as part of standard practice will share CPR quality measurements for patients enrolled in the trial with WCTU.

Where trial sites do not routinely collect quality of CPR data, these data will be collected for a subset of trial site participants using CPR cards, provided by the WCTU.

CE marked CPR cards, supplied by Laerdal Medical, will measure compression fraction, compression rate and depth. CPR cards are operated by switching on and placing centrally on the patient's chest. Chest compressions are then performed as usual. Quality of CPR data will be recorded during the resuscitation attempt but the card will not provide real-time feedback to the paramedics.

Up to 1,000 CPR cards will be distributed amongst trial sites. Trial trained paramedics will be taught how to use the CPR cards. Trial sites will use site specific processes to return used CPR cards from paramedics to site research teams. Site research teams will download data from the returned used CPR cards and provide the quality of CPR data securely to the WCTU.

4. ADVERSE EVENT MANAGEMENT

4.1 Definitions

4.1.1 Adverse events (AE)

An AE is: “Any untoward medical occurrence in a patient or clinical investigation participant taking part in health care research, which does not necessarily have a causal relationship with the research”.

4.1.2 Adverse Reactions (AR)

An AR is defined as any untoward and unintended response to the study IMP (adrenaline). A causal relationship between the trial treatment and an adverse event is at least a reasonable possibility, ie the relationship cannot be ruled out.

4.1.3 Serious Adverse Events (SAEs), Serious Adverse Reactions (SARs) and Suspected Unexpected Serious Adverse Events (SUSARs)

An AE or AR is considered serious if it:

- Results in death
- Is immediately life-threatening
- Requires hospitalisation or prolongation of existing hospitalisation
- Results in persistent or significant disability or incapacity
- Is a congenital anomaly or birth defect
- Is an important medical condition

A SAE is not thought to be causally related to the research.

A SAR is thought to be related but is expected.

SUSARs are SARs that are unexpected i.e their nature or severity is not consistent with the Summary of Product Characteristics.

4.2 Reporting SAEs and SUSARs

Events that are related to cardiac arrest and would be expected in patients undergoing attempted resuscitation should NOT be reported. These include:

- Death
- Hospitalisation
- Persistent or significant disability or incapacity
- Organ failure

All events categorised as serious (SAE/SAR/SUSAR) must be reported to WCTU within 24 hours of becoming aware of the event.

All reports of SAE/SAR/SUSAR will be reviewed on receipt by the Chief Investigators and those that are considered to satisfy the criteria for being related to the IMP and unexpected will be notified to the Main REC, MHRA and sponsor within 7 or 15 days of receipt in accordance with regulatory requirements. Reports of SAE/SAR/SUSAR will also be reviewed by the DMC at their regular meetings, or more frequently if requested by the DMC Chair.

4.3 Procedures in case of Pregnancy

Known pregnancy at the time of the cardiac arrest is an exclusion criterion for this trial however should the patient later be known to have been pregnant at the time of cardiac arrest and trial intervention then the following will apply:

Pregnancy itself is not regarded as an AE unless there is a suspicion that the investigational product under study may have interfered with the effectiveness of a contraceptive medication. However, the outcome of all pregnancies (spontaneous miscarriage, elective termination, normal birth or congenital abnormality) must be followed up and documented even if the subject was discontinued from the study.

All reports of congenital abnormalities/birth defects must be reported and followed up as a SAE.

4.4 End of the Trial

The trial will end when the last data is entered into the database which could be the last follow up visit or when HES data is received.

The trial will be stopped prematurely if:

- Mandated by the Ethics Committee (MREC)
- Mandated by the MHRA
- The TSC decides that recruitment should cease following recommendations from the DMC
- Funding for the trial ceases

The Main REC and MHRA will be notified in writing if the trial has been concluded or terminated early within 15 days.

5. DATA MANAGEMENT

Personal data collected during the trial will be handled and stored in accordance with the 1998 Data Protection Act and WCTU SOPs.

5.1 Data Collection and Management

The case report forms (CRFs) will be designed by the Trial Co-ordinator in conjunction with the Chief Investigator, ambulance services and Statistician.

Data from ambulance services will be entered into the trial database in anonymised format (identified by the arrest date and case number) for patients known to have died.

For survivors in hospital, personal identifiable information will be shared with WCTU, to allow future contact and follow-up. Handling of personal identifiable data will occur in accordance with WCTU SOPs.

Where we have not been able to collect data about the patients stay in hospital such as length of stay on ICU this will be collected from electronic datasets such as Intensive Care National Audit and Research Centre (ICNARC), and or Hospital Episode Statistics (HES), National Institute for Cardiovascular Outcomes Research (NICOR) and ONS mortality data. These data sets will also be used for the health economic analysis.

Survival status and health outcomes will be tracked through linkage (HSCIC) and hospital and/or GP records.

5.2 Database

The database will be set up by the Programming Team at WCTU and all specifications (i.e. database variables, validations checks, screens) will be agreed between the programmers, statistician and trial co-ordinator. The database will be tested and validated in accordance with the WCTU SOPs for secure data management.

5.3 Data Storage

All essential documentation and trial records will be stored by WCTU in conformance with the applicable regulatory requirements and access to stored information will be restricted to authorised personnel. Any paper data forms will be stored in a lockable filing cabinet in a secure room, to which access is restricted to authorised personnel. Electronic data will be stored in a secure area of the computer with access restricted to staff working on the trial. All databases containing identifiable information will be password protected. Any data that are transferred out of the secure environment (for example for statistical analysis, ICNARC, HES) will adhere to our unit SOPs.

5.4 Archiving

Trial documentation and data will be archived for at least ten years after completion of the trial. Electronic data sets will be stored indefinitely.

6. ANALYSIS

6.1 Statistical analysis

The primary analysis will be by intention to treat, comparing the outcomes between all participants randomised to adrenaline and all those randomised to placebo. The focus of the analysis will be on estimation of treatment effects and the uncertainty around them. A detailed statistical analysis plan will be developed by the trial statisticians and approved by the TSC and DMC.

Results will be presented as estimates of the treatment effect with 95% confidence intervals. Dichotomous outcomes (survival to 30 days, survived event, and survival to hospital discharge, 3, 6 and 12 months) will be analysed using logistic regression models, both unadjusted and adjusted for appropriate covariates. Survival and other time to event outcomes such as duration of hospital and ICU stay will be analysed using time to event techniques. Continuous outcomes (quality of life, cognition, anxiety/depression, posttraumatic stress) will be analysed by regression methods and the results presented as the difference in means between the groups and 95% confidence intervals. Modified Rankin Scale (a 7 category ordinal variable) will be analysed by ordinal logistic regression and the results will be presented using odds ratios and 95% confidence intervals. This will provide an increase in power over using a dichotomous outcome variable. Reporting of analyses will follow CONSORT guidelines.

The following exploratory analyses will be used to investigate potential modifiers of the treatment effect of adrenaline:

- Age
- Witnessed cardiac arrest versus not witnessed

- Bystander CPR versus no bystander CPR
- Type of initial rhythm (VF/VT, PEA, Asystole)
- Time of 999 call to administration of adrenaline
- Aetiology of cardiac arrest (presumed cardiac versus non-cardiac).

For categorical subgrouping variables we will fit interaction terms in logistic regression models to estimate the difference in treatment effects between the subgroups and the uncertainty around this. For continuous variables, we will fit the treatment-modifying factor as a covariate in regression models.

We will measure health related quality of life using EQ-5D at 3 and 6 months. We have selected 3 months for the timing of the initial measurement as studies indicate that neurological recovery plateaus from that time point. From the EQ-5D we can calculate health utilities for all participants, using standard tariffs. Patients who have died by 3 months will be attributed health utility of zero, and we will interpolate a value for any that die between 3 and 12 months. We will use methods of analysis developed by Goodacre et al 2012(47).

We will collect data on quality of CPR from across our trial sites and analyse all of the quality of CPR data collected.

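### Section 6.1 names no treatment-by-factor term for continuous modifiers, so as worded the age and time analyses cannot estimate effect modification

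*Protocol*

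**What the plan says.** Protocol section 6.1 (Statistical analysis) introduces a list of six factors with this aim: "The following exploratory analyses will be used to investigate potential modifiers of the treatment effect of adrenaline".

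Four of the six are given with their levels. Two examples are "Witnessed cardiac arrest versus not witnessed" and "Bystander CPR versus no bystander CPR"; initial rhythm has three named levels and aetiology has two. The other two, age and "Time of 999 call to administration of adrenaline", are listed without levels.

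The method follows in two consecutive sentences:

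- Categorical factors: "we will fit interaction terms in logistic regression models to estimate the difference in treatment effects between the subgroups", together with the uncertainty around that difference.
- Continuous factors: "For continuous variables, we will fit the treatment-modifying factor as a covariate in regression models".

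The second sentence mentions no interaction. The section also says that a detailed statistical analysis plan will be developed; that plan was not available here.

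**The concern.** The two sentences serve the same aim but name different devices, and only the first can meet it. An interaction term measures how far the treatment effect differs between levels of a factor. A covariate, in the ordinary sense that section 6.1 itself uses when it speaks of adjusted models, measures how the factor relates to outcome and leaves the treatment effect the same for everyone.

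An analyst who followed the text would report a coefficient for age and a coefficient for time under the heading of effect modification. Both would be prognostic. Older patients or longer delays could show clearly worse survival while adrenaline worked equally well, or equally badly, across the whole range. A reader could take such a coefficient as evidence of modification. Equally, the single treatment odds ratio could be taken as evidence that there is none. Neither reading would have support.

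**Working it through.** **Which factors are affected.** The protocol does not label any factor as continuous. Four of the six have stated levels and fall under the interaction sentence. Age and time from 999 call have none, so the covariate sentence applies to these two by elimination: 2 of 6.

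**Plan's own figures.** The protocol gives no figure for the modifier analyses. The nearest are the power figures in section 2.4.2. With 8,000 patients split 4,000 per arm (1:1 is an assumption) and a two-sided 0.05 test, power is 93.9% for 6% versus 8% (stated 93%) and 76.2% for 6% versus 7.5% (stated 75%). They reproduce, and they do not bear on this point.

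**Algebra.** Let T be treatment (0 or 1) and X the continuous factor.

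- Covariate model: logit(p) = b0 + b1·T + b2·X. The treatment log odds ratio at a given X is (b0 + b1 + b2·X) − (b0 + b2·X) = b1. It is the same at every X, and no parameter measures modification.
- Interaction model: logit(p) = b0 + b1·T + b2·X + b3·T·X. The treatment log odds ratio is b1 + b3·X, and b3 is the modification per unit of X.

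This result depends on no assumed effect size.

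**Illustration.** 300 simulated trials per scenario, n = 8,000, 4,000 per arm. X is a standardised factor such as age. The true model is logit(p) = −2.75 − 0.4·X + b3·T·X. The intercept gives 1/(1 + e^2.75) = 6.0% survival at X = 0, in line with the 6% of section 2.4.1. The slope of −0.4 per SD and the values of b3 are assumptions made for illustration.

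| True b3 | True treatment OR at −1 SD / +1 SD | Covariate model: single treatment OR | Covariate model: X coefficient (share significant) | Interaction model: mean b3 (share significant) |
|---|---|---|---|---|
| 0 | 1.00 / 1.00 | exp(−0.001) = 1.00 | −0.397 (100%) | −0.003 (4%) |
| +0.3 | 0.74 / 1.35 | exp(−0.070) = 0.93 | −0.249 (100%) | +0.304 (89%) |
| −0.3 | 1.35 / 0.74 | exp(0.133) = 1.14 | −0.552 (100%) | −0.297 (90%) |

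The true odds ratios at ±1 SD are exp(±0.3) = 1.35 and 0.74.

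The covariate model's X coefficient is significant in every replicate of all three scenarios, including the one with no modification, so its significance carries no information on the question. The interaction model recovers b3 in each scenario and rejects at about the nominal rate when b3 is zero.

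**Does another section supply the missing term?** Section 6.3 (Economic Evaluation) plans interactions between treatment and covariates, age among them, but in a net-benefit regression. That concerns cost-effectiveness and does not change the survival or neurological analyses of section 6.1.

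**The case against.** The strongest defence is that the wording is loose rather than wrong. The text does not say that the factor enters solely as a main effect. The sentence calls it a treatment-modifying factor, and the stated aim is effect modification. The authors may have meant that categorical factors give contrasts between subgroups while continuous factors stay uncategorised, with the interaction understood. The statistical analysis plan may say so. This lowers the certainty about intent, but it does not remove the defect. The preceding sentence shows that the authors name interaction terms when they want them. Nor is this a detail left for later: the protocol states a method, and the stated method does not meet its aim. If the analysis plan does specify interactions, the two documents differ and the protocol sentence still needs correcting.

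It might also be said that risk differences vary with X even in a main-effects logistic model. They do, but the variation comes from the logit link and is not estimated from the data as modification.

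Three stronger readings are tempting and are not supported:

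- *No contrast by time can be formed, because placebo patients receive no adrenaline.* Read literally, the label has no meaning in the placebo arm. But the trial is double blind with identical pre-filled syringes (sections 2.9.1, 2.10.1 and 2.10.2), and trial IMP takes the place of standard adrenaline (section 2.10). The event that crews can record is administration of trial drug in either arm, so the label is shorthand and needs only a correction of wording.
- *Timing is one of the trial's scientific questions, on the strength of section 2.6.5.* That section is part of the ethical case for enrolment without prior consent and reports what observational studies suggest. The research question (1.2) and objectives (2.2) do not mention timing, and section 1.3 says that it would be difficult to control for in a randomised trial. It enters the analysis only as an exploratory factor.
- *The simulated sizes predict what this trial would miss.* They illustrate the algebra under assumed values and say nothing about how much modification exists here.

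**Conclusion.** The point holds. As worded, two of the six exploratory modifier analyses cannot estimate effect modification, because the sentence that governs them names a main-effect covariate and no product term. This rests on two inferences from the text: that age and time are the continuous factors, and that covariate has its ordinary meaning. Both are well supported by the layout of the list and by the contrast between the two method sentences.

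Severity is moderate. A reader might infer that the trial's main conclusions are at risk. They are not: these analyses are labelled exploratory, and the primary intention-to-treat comparison, the sample size and the interim monitoring do not depend on this sentence.

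**What to change.** Replace the sentence on continuous variables in section 6.1 with: *For continuous variables we will keep the factor continuous and fit a treatment-by-factor interaction term, reporting the interaction estimate with its 95% CI.* A check of linearity, for example with a spline, is optional and can be left to the statistical analysis plan.

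As a wording correction, define the time factor identically in both arms as 999 call to first administration of trial IMP. Section 2.7 expects a few eligible patients whose pack is opened but who receive no dose. They have no value for this factor and should be reported as such. Pack-opening time should not stand in for them: that would mix two quantities in one variable, and the protocol does not say that a clock time of opening is recorded.

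The cost is one sentence and one label. Age needs no new data. The time factor needs the time of first dose, which the listed analysis already presupposes, although the protocol does not state explicitly that it is captured; this should be confirmed.

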2.3 Outcome Measures

2.3.1 Efficacy

Primary outcome:

Survival to 30 days post cardiac arrest.

Secondary outcomes:

1. Survived event (*sustained ROSC, with spontaneous circulation until admission and transfer of care to medical staff at the receiving hospital*)
2. Survival to hospital discharge (*the point at which the patient is discharged from the hospital acute care unit regardless of neurological status, outcome or destination*) 3, 6 and 12 months
3. Neurological outcome (modified Rankin Scale (mRS)) at hospital discharge, 3 and 6 months
4. Neurological outcomes (IQCODE and "Two simple questions") at 3 and 6 months
5. Health related quality of life at 3 and 6 months (SF12 and EQ-5D)
6. Cognitive outcome at 3 months (Mini Mental State Examination (MMSE))

7. Anxiety and depression at 3 months (Hospital Anxiety and Depression Scale (HADS))
8. Post Traumatic Stress at 3 months (PTSD civilian checklist (PCL-C))
9. Hospital length of stay
10. Intensive care length of stay

The outcomes defined by the Utstein convention for reporting outcomes from cardiac arrest (34) will be reported.

mRS will be measured at hospital discharge, 3 and 6 months. mRS was selected over Cerebral Performance Category (CPC) as it is more sensitive to detect mild cognitive impairment. It can be reliably extracted from medical records and is a predictor of long term survival. There is emerging international consensus (Utstein 2012/2013) that mRS should be the primary measure of neurological outcome in cardiac arrest trials. mRS is a 7 point scale ranging from mRS 0 (no symptoms) to 6 (dead). The spectrum of impairment of health related quality of life following cardiac arrest includes memory and cognitive dysfunction, affective disorders PTSD(35). The number of patients expected to survive to hospital discharge is anticipated to be in the region of 400-600, which will allow more intensive follow-up. The SF-12 is a standard quality of life measure that is short and easy to complete. In addition the EQ-5D will be used as a health utility measure for the health economic analysis.

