2.4 Sample Size

2.4.1 Incidence of primary outcome

Most existing data refer to survival to hospital discharge rather than survival to 30 days, but as most mortality will occur in the first days after cardiac arrest, we expect these two measures to be very similar. Estimates of long-term survival of patients who receive adrenaline during a resuscitation attempt vary between about 3.5% and 12%. From national data for England, overall survival to hospital discharge of patients for whom resuscitation is attempted is 7%(1). However, this will include a small number of patients who achieve ROSC immediately and would not receive adrenaline, hence would not be recruited to the trial. As these patients have much better outcomes, the survival among the trial population will be slightly lower. Estimates from the Norwegian trial of intravenous drugs and the Australian trial of adrenaline were 9%(10) and 4%(9) respectively. In the PARAMEDIC trial, survival for patients who received adrenaline is 6%, and in the REVIVE airways study, where most patients will have received adrenaline, it is 8.5% (personal communication [name]). We therefore expect survival to 30 days of approximately 6% in the adrenaline group.

The trial's primary aim is to estimate the treatment effect of adrenaline and the uncertainty around this; we have therefore based the target sample size primarily on the precision of the estimate of the risk ratio(40). Figure 4 shows the precision that is achievable (width of the 95% confidence interval for the risk ratio) with different total sample sizes, for risk ratios (placebo versus adrenaline) of 1.25 and 1.00. A risk ratio of 1.25 corresponds to an increase in 30-day survival from 6% in the adrenaline group to 7.5% in the placebo group.

[figure not shown]

Fig. 4. Width of 95% confidence interval for the risk ratio against sample size, for RR 1.25 (left) and RR 1.0 (right), with 6% survival in the adrenaline arm.

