2.4.2 Sample size

The target sample size will be 8,000, which is expected to give a width of the 95% CI for the risk ratio of approximately 0.4 or slightly less; for a risk ratio of 1.25 the 95% CI is 1.07 to 1.46, and for risk ratio of 1.0 it is 0.84 to 1.19. There is a trade-off between precision and practicality in setting a target sample size; above 8,000, there is only a small improvement in precision, but the difficulty and time needed to recruit this number increase significantly. We expect a very small amount of missing data for survival outcomes; in PARAMEDIC we have ascertained survival status for over 99% of randomised patients, and we have therefore not adjusted the sample size estimates to account for missing data.

Using a conventional sample size calculation based on a significance test, a sample size of 8,000 would have 93% power to achieve a statistically significant ($p < 0.05$) result if the true treatment difference is a risk ratio of 1.33 (increase from 6% in adrenaline group to 8% in placebo group), or 75% power if the true treatment difference is a risk ratio of 1.25 (increase from 6% to 7.5%).

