6.3 Economic Evaluation

An economic evaluation will be integrated into the trial design. The economic evaluation will be conducted from the recommended NHS and personal social services (PSS) perspective (48). Data will be collected on the health and social service resources used in the treatment of each trial participant during the period between randomisation and six months post-randomisation. Resource utilisation data will be collected through four principal means: (i) use of trial interventions, concurrent treatments, mode and distance of initial transportation and subsequent transfers, will be estimated using the computerised data collection systems developed for the PARAMEDIC trial; (ii) detailed information on ITU resource utilisation and specific treatments (e.g. cardiovascular support, therapeutic hypothermia use) will be collected using bespoke trial data collection forms; this information will in turn be validated, and where necessary complemented, using information

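### Differences in MMSE, HADS, PCL-C and SF-12 means, available only from consenting survivors, are presented as treatment effects; the utility rule for later deaths also needs its endpoints stated

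*Protocol*

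**What the plan says.** Protocol section 6.1 opens with an intention-to-treat primary analysis of all randomised participants and says that results will be given as treatment-effect estimates with 95% confidence intervals. In the same paragraph: "Continuous outcomes (quality of life, cognition, anxiety/depression, posttraumatic stress) will be analysed by regression methods and the results presented as the difference in means". No rule for patients who have died accompanies that sentence.

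The scales are collected from a much smaller group. Section 3.2.3 follows up survivors who are willing to take part. Section 2.3.1 lists "Health related quality of life at 3 and 6 months (SF12 and EQ-5D") and places MMSE, HADS and PCL-C at 3 months. Section 2.2.2 describes the cognitive and neurological objective as concerning survivors.

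Other outcomes do have a rule for death. In section 2.3.1 the mRS runs to 6, which is death, and section 6.1 analyses it as an ordinal scale. For EQ-5D utility, section 6.1 gives zero to anyone dead by 3 months and then says "we will interpolate a value for any that die between 3 and 12 months". EQ-5D is measured at 3 and 6 months only, and section 6.3 collects resource use "during the period between randomisation and six months post-randomisation".

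**The concern.** Being alive to complete a questionnaire is an outcome of this trial, and survival to 30 days is the primary one. Randomisation balances the arms at the point of enrolment. It does not balance the patients still alive at 3 months if adrenaline affects who they are. A difference in survivor means then mixes two things: any effect on patients who would survive on either arm, and a difference in which patients survived. Called a treatment effect in a section that opens with an all-randomised comparison, it could be published and read as a randomised finding about adrenaline and cognition or mood.

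The utility sentence raises a smaller matter. It does not say between which points a value is interpolated. A patient who dies in month 4 is dead at month 6. Under one reading that patient could still be given a positive value there; under another, the sentence describes only the path from the last measurement down to death.

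**Working it through.** **Inputs from the protocol**
- Section 2.4.2: "The target sample size will be 8,000". I take 4,000 per arm; the text does not state the ratio, so 1:1 is an assumption.
- Section 2.4.1: "We therefore expect survival to 30 days of approximately 6% in the adrenaline group", and "A risk ratio of 1.25 corresponds to an increase in 30-day survival from 6% in the adrenaline group to 7.5% in the placebo group".
- Section 2.1.1: a pilot target of more than 75% of living patients agreeing to follow-up.
- Section 2.3.1: 400 to 600 patients expected to survive to discharge.

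**The plan's own figures**
- Power at two-sided 0.05 (two-sided assumed) with 4,000 per arm: 76.2% for 6% v 7.5% (stated 75%) and 93.9% for 6% v 8% (stated 93%). Both reproduce within 2 points.
- Expected survivors: 4,000 × 0.06 + 4,000 × 0.075 = 240 + 300 = 540, inside the stated 400 to 600.

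**Who supplies scale data**
- All survivors: 540 / 8,000 = 6.75% of those randomised.
- At 75% uptake: 0.75 × 240 = 180 and 0.75 × 300 = 225, together 405, or 405 / 8,000 = 5.1%.

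**Share of survivors without a counterpart**
- At 7.5%: (300 − 240) / 300 = 20% of survivors in the better-surviving arm.
- At 8%: (320 − 240) / 320 = 25%.
- This takes everyone who survives in one arm as someone who would also survive in the other. If treatment saves some and loses others, the share without a counterpart is larger.

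**Shift in survivor means with no effect on any patient who would survive on either arm**

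Shift = share of extra survivors × their gap from other survivors. The gaps are assumed.

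| Gap (SD) | Shift at 6% v 7.5% | Shift at 6% v 8% |
|---|---|---|
| 0.25 | 0.05 | 0.06 |
| 0.5 | 0.10 | 0.13 |
| 1.0 | 0.20 | 0.25 |

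On the MMSE, suppose patients who would survive on either arm average 26 and the extra survivors average x (both assumed). The shift is (6.0 × 26 + 1.5 × x) / 7.5 − 26, which gives −0.8, −1.6 and −2.4 points for x = 22, 18 and 14. In this scenario the extra survivors are on placebo, so placebo would look worse.

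**Would such a shift be noticed?** With 240 and 300 patients the standard error of the difference is √(1/240 + 1/300) = 0.087 SD. With 180 and 225 it is √(1/180 + 1/225) = 0.10 SD. A shift of 0.20 SD would reach p < 0.05 with probability 64% and 52% respectively; a shift of 0.10 SD, with probability 21% and 17%.

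**Utility sentence, taking the reading in which a dead patient keeps a positive value**

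Assume that 3% to 15% of the 540 die late and carry 0.2 to 0.5 instead of 0.
- Patients affected: 540 × 0.03 = 16 to 540 × 0.15 = 81.
- Mean utility over all 8,000: 16.2 × 0.2 / 8,000 = 0.0004 to 81 × 0.5 / 8,000 = 0.005.
- Difference between arms, with the same late-death proportion in each: 60 × 0.03 × 0.2 / 4,000 = 0.0001 to 60 × 0.15 × 0.5 / 4,000 = 0.001.

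The base is 30-day survivors, and deaths after month 6 are counted although they fall outside a 6-month horizon, so these counts lean high.

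**The case against.** The restriction to survivors is not hidden. Section 2.2.2 says so in the objective and section 3.2.3 says so for follow-up. These are secondary outcomes, and a statistical analysis plan commonly sets the population and caveats for such scales. That stands as mitigation. It does not remove the point, because section 6.1 itself fixes the estimator, calls the results treatment effects and offers no caveat for these scales.

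A reader might infer that death is mishandled across all follow-up outcomes. The protocol does not support that: mRS counts death as its worst category, EQ-5D scores deaths by 3 months as zero, and survival is defined for everyone.

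A reader might also infer that survivor means would make adrenaline look harmful. The background describes better short-term survival on adrenaline with doubt about long-term outcome, while the sample-size scenario has more 30-day survivors on placebo. On those figures poorer-scoring extra survivors would count against placebo. The direction is open, and so is whether treatment changes who survives at all; the trial is testing that.

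On utilities, a reader might infer that the plan credits quality-adjusted life to dead patients, always upwards, or that interpolation is impossible without a 12-month EQ-5D. Neither follows. Death, valued at zero in the same sentence, is a natural second anchor, and a line from the last measurement to zero at death is an ordinary area-under-the-curve step. What stands is that the endpoints are not stated.

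**Conclusion.** The point holds for MMSE, HADS, PCL-C and SF-12. As written, section 6.1 would report as treatment effects comparisons that rest on about 5% to 7% of those randomised, selected after randomisation by survival and then by consent. At 6% v 7.5%, one in five survivors in the better-surviving arm has no counterpart. Under the assumed gaps, the survivor means differ by 0.05 to 0.20 SD with no effect on anyone who would survive on either arm.

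The 540 and the 20% rest on the protocol's survival figures and on 1:1 allocation; the 405 also needs 75% uptake in each arm. The size of the shift rests on assumed gaps and can run against either arm. If treatment does not alter who survives, this bias from survival does not arise.

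The utility sentence is a minor ambiguity. Its effect on the between-arm difference is about 0.0001 to 0.001 under assumed inputs, and its direction depends on how the sentence is read.

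**What to change.** In section 6.1, take MMSE, HADS, PCL-C and SF-12 out of the general treatment-effect wording. State that they are summarised by arm among patients alive and assessed, that the comparison is conditional on survival and descriptive, and that the numbers randomised, alive and assessed are shown per arm at each time point. State that randomised claims rest on outcomes already in the plan and defined for everyone: survival, ordinal mRS with 6 as death, and EQ-5D utility or QALYs with death at zero.

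In the utility paragraph, state that utility is zero from the date of death for every death, that interpolation runs only between the last EQ-5D measurement and death, and that the within-trial horizon matches the 3- and 6-month EQ-5D and the 6-month resource data. Align section 6.3 with this.

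The cost is wording. No new follow-up is needed, because survival is already tracked to 12 months (section 2.8 and Table 1). The downside is that the survivor scales lose the status of treatment effects.
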